28. BREACH OF CONFIDENTIALITY

One of the risks is release of information from health or research records in a way that violates privacy rights. The investigators will protect records so that name, address, phone number, and any other information that identifies the participant will be kept private. It will be stated to the participant that the chance that this information will be given to an unauthorized individual without the participant's permission is very small.

29. POTENTIAL BENEFITS TO SUBJECTS

We hypothesize that the combination of ruxolitinib and enasidenib in patients with MPN both in accelerate/blasts-phase as well as with high risk chronic phase myelofibrosis with an IDH2 mutation will improve the overall clinical response to therapy including complete response, partial response, complete and partial blasts response, symptomatic improvement and improvement in quality of life.

30. SHARING OF RESULTS WITH SUBJECTS

Results of tests performed during the study will be shared with the subject. Results of biomarker correlates will not be shared.

31. PRIOR APPROVALS

Approval to commence research will be obtained initially at Mount Sinai through the usual protocol approval pathway including the Disease Focus Group, Resource Allocation and Evaluation, Protocol Review and Monitoring Committees. Once this is complete, the protocol will be submitted for an IND to the Food and Drug Administration. The IND-approved protocol will then be submitted to the central SMART IRB (BRANY) for ethical and regulatory evaluation. Once this is IRB approved the final contract (with budget) will be executed and a Site Initiation Visit (SIV) will be scheduled. This will then allow for Mount Sinai to activate the protocol and start enrollment. The BRANY approved protocol will be concurrently submitted for internal review at the other MPN-RC participating sites. SIVs will

in Patients with Accelerated/Blast-phase Myeloproliferative Neoplasm or Chronicphase Myelofibrosis with an IDH2 Mutation

(Myeloproliferative Neoplasms Research Consortium [MPN-RC] 119)

be scheduled at each site once the protocol is approved locally. This will be coordinated throughout the MPN-RC central office within Project 4.

32. ECONOMIC BURDEN TO SUBJECTS

There will be no additional costs to the subject to participate in the study beside the standard of care costs. Research related per patient costs will be covered by the MPN-RC and will be determined by Medicare Analysis review (MCA).

33. CONSENT PROCESS

MPN-

Before protocol-specified procedures are carried out, consenting professionals will explain full details of the protocol and study procedures as well as the risks involved to participants prior to their inclusion in the study. Participants will also be informed that they are free to withdraw from the study at any time. All participants must sign an IRB/PB-approved consent form indicating their consent to participate. This consent form meets the requirements of the Code of Federal Regulations and the Institutional Review Board/Privacy Board of each site. The consent form will include the following:

- 1. The nature and objectives, potential risks and benefits of the intended study.
- 2. The length of study and the likely follow-up required.
- 3. Alternatives to the proposed study. (This will include available standard and investigational therapies. In addition, patients will be offered an option of supportive care for therapeutic studies.)
- 4. The name of the Investigator(s) responsible for the protocol.
- 5. The right of the participant to accept or refuse study interventions/interactions and to withdraw from participation at any time.

Before any protocol-specific procedures can be carried out, the consenting professional will fully explain the aspects of patient privacy concerning research specific information.

Each participant and consenting professional will sign the consent form. The participant must receive a copy of the signed informed consent form. The consent process should be documented in the patients' medical records.

A Phase II Open-label Study of Combined Ruxolitinib and Enasidenib Sinai in Patients with Accelerated/Blast-phase Myeloproliferative Neoplasm or Chronic-

phase Myelofibrosis with an IDH2 Mutation

(Myeloproliferative Neoplasms Research Consortium [MPN-RC] 119)

34.1 APPENDIX A: RESPONSE CRITERIA

Complete Response	As per 2013 IWG-MRT and ELN Criteria
Partial Response	As per 2013 IWG-MRT and ELN Criteria
Clinical Improvement (CI)	As per 2013 IWG-MRT and ELN Criteria
Anemia Response	As per 2013 IWG-MRT and ELN Criteria
Spleen Response	As per 2013 IWG-MRT and ELN Criteria
Symptom Response	As per 2013 IWG-MRT and ELN Criteria
Progressive Disease	 After at least 3 cycles of combined therapy: New splenomegaly that is palpable at least 5cm below the LCM a ≥100% increase in palpable distance, below LCM, for baseline splenomegaly of 5-10cm or a 50% increase in palpable distance, below LCM, for baseline splenomegaly of > 10cm Progression from chronic-phase disease (< 10% blasts) to blast-phase (≥ 20% blasts) disease on two separate CBCs within 28 days For patients in accelerated of blast phase disease at baseline, a doubling of the absolute blast count
Stable Disease	As per 2013 IWG-MRT and ELN Criteria
Cytogenetic Remission	As per 2013 IWG-MRT and ELN Criteria
Molecular Remission	 Complete Molecular remission: eradication of IDH2 and JAK2/MPL/CALR mutations as assessed by both next-generation sequencing and digital PCR assays. Partial Molecular remission: 50% reduction in mutant IDH2 and JAK2/MPL/CALR allele burden as assessed by next-generation sequencing
Cytogenetic/Molecular Relapse	As per 2013 IWG-MRT and ELN Criteria
Complete Blast Response	Absence of circulating peripheral blood blast count with residual features of chronic-phase MPN maintained for at least 28 consecutive days.
Partial Blast Response	Reduction to <4% blast count in peripheral blood with residual features of chronic-phase MPN maintained for at least 28 consecutive days.

A Phase II Open-label Study of Combined Ruxolitinib and Enasidenib Sinai in Patients with Accelerated/Blast-phase Myeloproliferative Neoplasm or Chronic-

phase Myelofibrosis with an IDH2 Mutation

(Myeloproliferative Neoplasms Research Consortium [MPN-RC] 119)

34.2 **APPENDIX B: IWG-MRT AND ELN RESPONSE CRITERIA**

Response categories	Required criteria (for all response categories, benefit must last for ≥12 wk to qualify as a response)
CR	Bone marrow:*Age-adjusted normocellularity; <5% blasts; ≤grade 1 MF† and
	Peripheral blood: Hemoglobin \geq 100 g/L and <unl; <math="" count="" neutrophil="">\geq 1 \times 10⁹/L and <unl;< td=""></unl;<></unl;>
	Platelet count \geq 100 \times 10 ⁹ /L and $<$ UNL; <2% immature myeloid cells‡ and
	Clinical: Resolution of disease symptoms; spleen and liver not palpable; no evidence of EMH
PR	Peripheral blood: Hemoglobin \geq 100 g/L and $<$ UNL; neutrophil count \geq 1 \times 10 ⁹ /L and $<$ UNL; platelet count \geq 100 \times 10 ⁹ /L and $<$ UNL; platelet count \geq 100 \times 10 ⁹ /L and $<$ UNL; platelet count \geq 100 \times 10 ⁹ /L and $<$ UNL; platelet count \geq 100 \times 10 ⁹ /L and $<$ UNL; platelet count \geq 100 \times 10 ⁹ /L and $<$ UNL; platelet count \geq 100 \times 10 ⁹ /L and $<$ UNL; platelet count \geq 100 \times 10 ⁹ /L and $<$ UNL; platelet count \geq 100 \times 10 ⁹ /L and $<$ UNL; platelet count \geq 100 \times 10 ⁹ /L and $<$ UNL; platelet count \geq 100 \times 10 ⁹ /L and $<$ UNL; platelet count \geq 100 \times 10 ⁹ /L and $<$ UNL; platelet count \geq 100 \times 10 ⁹ /L and $<$ UNL; platelet count \geq 100 \times 10 ⁹ /L and $<$ UNL; platelet count \geq 100 \times 10 ⁹ /L and $<$ UNL; platelet count \geq 100 \times 10 ⁹ /L and $<$ UNL; platelet count \geq 100 \times 10 ⁹ /L and $<$ UNL; platelet count \geq 100 \times 10 ⁹ /L and $<$ UNL; platelet count \geq 100 \times 10 ⁹ /L and $<$ UNL; platelet count \geq 100 \times 10 ⁹ /L and $<$ UNL; platelet count \geq 100 \times 10 ⁹ /L and $<$ UNL; platelet count \geq 100 \times 10 ⁹ /L and $<$ UNL; platelet count \geq 100 \times 10 ⁹ /L and $<$ UNL; platelet count \geq 100 \times 10 ⁹ /L and $<$ UNL; platelet count \geq 100 \times 10 ⁹ /L and $<$ UNL; platelet count \geq 100 \times 10 ⁹ /L and $<$ UNL; platelet count \geq 100 \times 10 ⁹ /L and $<$ UNL; platelet count \geq 100 \times 10 ⁹ /L and $<$ UNL; platelet count \geq 100 \times 10 ⁹ /L and $<$ UNL; platelet count \geq 100 \times 10 ⁹ /L and $<$ UNL; platelet count \geq 100 \times 10 ⁹ /L and $<$ UNL; platelet count \geq 100 \times 10 ⁹ /L and $<$ UNL; platelet count \geq 100 \times 10 ⁹ /L and $<$ UNL; platelet count \geq 100 \times 10 ⁹ /L and $<$ UNL; platelet count \geq 100 \times 10 ⁹ /L and $<$ UNL; platelet count \geq 100 \times 10 ⁹ /L and $<$ UNL; platelet count \geq 100 \times 10 ⁹ /L and $<$ UNL; platelet count \geq 100 \times 10 ⁹ /L and $<$ UNL; platelet count \geq 100 \times 10 ⁹ /L and $<$ UNL; platelet count \geq 100 \times 10 ⁹ /L and $<$ UNL; platelet count \geq 100 \times 10 ⁹ /L and $<$ UNL; platelet count \geq 100 \times 10 ⁹ /L and $<$ UNL; platelet count \geq 10 ⁹ /L and $<$ UNL; platelet count \sim 10 ⁹ /L and $<$ UNL; platelet count $<$ 1
	<unl; <2%="" and<="" cells‡="" immature="" myeloid="" td=""></unl;>
	Clinical: Resolution of disease symptoms; spleen and liver not palpable; no evidence of EMH or
	Bone marrow:* Age-adjusted normocellularity; <5% blasts; ≤grade 1 MF†, and peripheral blood: Hemoglobin ≥85 but <100 g/L and <unl; 109/L and <unl; 10<sup="" <100="" but="" count="" platelet="" ×="" ≥50,="">9/L and <unl; <2%="" immature="" myeloid<="" td=""></unl;></unl;></unl;>
	cells‡ and
	Clinical: Resolution of disease symptoms; spleen and liver not palpable; no evidence of EMH
Clinical improvement (CI)	The achievement of anemia, spleen or symptoms response without progressive disease or increase in severity of anemia, thrombocytopenia, or neutropenia§
Anemia response	Transfusion-independent patients: a \geq 20 g/L increase in hemoglobin levell
	Transfusion-dependent patients: becoming transfusion-independent
Spleen response#	A baseline splenomegaly that is palpable at 5-10 cm, below the LCM, becomes not palpable** or
	A baseline splenomegaly that is palpable at >10 cm, below the LCM, decreases by \geq 50%**
	A baseline splenomegaly that is palpable at <5 cm, below the LCM, is not eligible for spleen response
	A spleen response requires confirmation by MRI or computed tomography showing ≥35% spleen volume reduction
Symptoms response	A ≥50% reduction in the MPN-SAF TSS11
Progressive disease‡‡	Appearance of a new splenomegaly that is palpable at least 5 cm below the LCM or
	A \ge 100% increase in palpable distance, below LCM, for baseline splenomegaly of 5-10 cm or
	A 50% increase in palpable distance, below LCM, for baseline splenomegaly of >10 cm or
	Leukemic transformation confirmed by a bone marrow blast count of ≥20% or
	A peripheral blood blast content of \geq 20% associated with an absolute blast count of \geq 1 × 10(9)/L that lasts for at least 2 weeks
Stable disease	Belonging to none of the above listed response categories
Relapse	No longer meeting criteria for at least CI after achieving CR, PR, or CI, or
	Loss of anemia response persisting for at least 1 month or
	Loss of spleen response persisting for at least 1 month
	Recommendations for assessing treatment-induced cytogenetic and molecular changes
Cytogenetic remission	At least 10 metaphases must be analyzed for cytogenetic response evaluation and
	requires confirmation by repeat testing within 6 months window
	CR: eradication of a preexisting abnormality
	PR: ≥50% reduction in abnormal metaphases
	(partial response applies only to patients with at least ten abnormal metaphases at baseline)
Molecular remission	Molecular response evaluation must be analyzed in peripheral blood granulocytes and
	requires confirmation by repeat testing within 6 months window
	CR: Eradication of a pre-existing abnormality
	PR: ≥50% decrease in allele burden
	(partial response applies only to patients with at least 20% mutant allele burden at baseline)
Cytogenetic/molecular relapse	Re-emergence of a pre-existing cytogenetic or molecular abnormality that is confirmed by repeat testing

EMH, extramedullary hematopoiesis (no evidence of EMH implies the absence of pathology- or imaging study-proven nonhepatosplenic EMH); LCM, left costal margin; UNL, upper normal limit

*Baseline and posttreatment bone marrow slides are to be interpreted at one sitting by a central review process. Cytogenetic and molecular responses are not required for CR assignment.

+Grading of MF is according to the European classification

Thiele et al. European consensus on grading bone marrow fibrosis and assessment of cellularity. Haematologica, 2005;90:1128.

It is underscored that the consensus definition of a CR bone marrow is to be used only in those patients in which all other criteria are met, including resolution of leukoerythroblastosis It should also be noted that it was a particularly difficult task for the working group to reach a consensus regarding what represents a complete histologic remission

#Immature myeloid cells constitute blasts + promyelocytes + myelocytes + metamyelocytes + nucleated red blood cells. In splenectomized patients, <5% immature myeloid cells is allowed.

§See above for definitions of anemia response, spleen response, and progressive disease. Increase in severity of anemia constitutes the occurrence of new transfusion dependency or a >20 g/L decrease in hemoglobin level from pretreatment baseline that lasts for at least 12 weeks. Increase in severity of thrombocytopenia or neutropenia is defined as a 2-grade decline, from pretreatment baseline, in platelet count or absolute neutrophil count, according to the Common Terminology Criteria for Adverse Events (CTCAE) version 4.0. In addition, assignment to CI requires a minimum platelet count of ≥25 000 × 10(9)/L and absolute neutrophil count of ≥0.5 × 10(9)/L

IIApplicable only to patients with baseline hemoglobin of <100 g/L. In patients not meeting the strict criteria for transfusion dependency at the time of study (see as follows), but have received transfusions within the previous month, the pretransfusion hemoglobin level should be used as the baseline. ¶Transfusion dependency before study enrollment is defined as transfusions of at least 6 units of packed red blood cells (PRBC), in the 12 weeks prior to study

enrollment, for a hemoglobin level of <85 g/L, in the absence of bleeding or treatment-induced anemia. In addition, the most recent transfusion episode must have occurred in the 28 days prior to study enrollment. Response in transfusion-dependent patients requires absence of any PRBC transfusions during any consecutive "rolling" 12-week interval during the treatment phase, capped by a hemoglobin level of ≥85 g/L.

#In splenectomized patients, palpable hepatomegaly is substituted with the same measurement strategy.

*Spleen or liver responses must be confirmed by imaging studies where a ≥35% reduction in spleen volume, as assessed by MRI or CT, is required. Furthermore, ⇒Spleet of liver responses must be committed by integring acues where a =25% reduction in spleet volume, to access of your of or a required, a statistical access of the spleet of liver access of the spleet of liv

inactivity, night sweats, itching, bone pain, abdominal discomfort, weight loss, and fevers. Scoring is from 0 (absent/as good as it can be) to 10 (worst imaginable/as bad as it can be) for each item. The MPN-SAF TSS is the summation of all the individual scores (0-100 scale). Symptoms response requires ≥50% reduction in the MPN-SAF TSS. #Progressive disease assignment for splenomegaly requires confirmation my MRI or computed tomography showing a =25% increase in spleen volume from baseline. eline values for both physical examination and imaging studies refer to pretreatment baseline and not to posttreatment measurements.

A Phase II Open-label Study of Combined Ruxolitinib and Enasidenib Sinai in Patients with Accelerated/Blast-phase Myeloproliferative Neoplasm or Chronic-

phase Myelofibrosis with an IDH2 Mutation

(Myeloproliferative Neoplasms Research Consortium [MPN-RC] 119) 34.3 APPENDIX C: MEDICATIONS KNOWN TO PROLONG THE QT INTERVAL

amiodarone	citalopram	Escitalopram	methadone	sevoflurane
astemizole	clarithromycin	Flecainide	moxifloxacin	sotalol
azithromycin	disopyramide	Halofantrine	pentamidine	sparfloxacin
bepridil	dofetilide	Haloperidol	pimozide	terfenadine
chloroquine	domperidone	Ibutilide	probucol	thioridazine
chlorpromazine	droperidol	Levomethadyl	procainamide	
cisapride	erythromycin	Mesoridazine	quinidine	

MPN-RC

A Phase II Open-label Study of Combined Ruxolitinib and Enasidenib Sinai The Ti in Patients with Accelerated/Blast-phase Myeloproliferative Neoplasm or Chronic-

phase Myelofibrosis with an IDH2 Mutation (Myeloproliferative Neoplasms Research Consortium [MPN-RC] 119)

34.4 APPENDIX D: GUIDANCE IDH-INHIBITOR DIFFERENTIATION SYNDROME (IDH-DS) GUIDANCE FOR MANAGEMENT OF DIFFERENTIATION SYNDROME IN SUBJECTS WITH HEMATOLOGIC MALIGNANCIES TREATEDWITH IDH-INHIBITORS

The participating investigators/health care professionals are responsible for the appropriate evaluation and management of the safety related issues in subjects enrolled in the study. The approach outlined below for identifying and managing Differentiation Syndrome in patients treated with IDH inhibitors should be considered as guidance and therefore management of each case should be individualized, as appropriate.

Introduction to IDH inhibitors Differentiation Syndrome

MPN

The isocitrate dehydrogenase (IDH) mutation, found in up to 15% of subjects with AML^{36,37}, leads to excess accumulation of 2-hydroxyglutarate (2-HG) that causes inhibition of dioxygenase dependent enzymes responsible for demethylation of DNA and histones, and consequently resulting in impaired bone marrow differentiation^{39,40}.

Direct inhibition of mutated protein activity by IDH inhibitor is intended to block abnormal production of the oncogenic metabolite 2-HG and impact clinical outcome through a variety of mechanisms that include restoration of differentiation of the malignant cells.

In patients with hematologic malignancies, initiation of treatment with the differentiating agents, such as IDH inhibitors, and associated maturation of aberrant bone marrow, may alter the balance of the expression of adhesion molecules and chemoattractants (cytokines) that could mediate tissue infiltration by maturing blood cells⁴⁴, associated with signs and symptoms of Differentiation Syndrome (DS).

Signs and symptoms could include fever, dyspnea, edema/ weight gain, increased serum creatinine and, in some cases, clinical features consistent with the acute respiratory distress syndrome with associated bilateral pulmonary infiltrates, and pulmonary or pericardial effusions. Increases in white blood cell (WBC) count concurrent to DS has been observed, but by itself do not substantiate the syndrome.

There is no pathognomonic clinical sign or laboratory test to diagnose DS. In some instances, clinical presentation of DScan be confounded by other medical condition(s), such as concurrent infections or heart failure. Consequently, diagnosis of DS is made by excluding other potential causes, rather than based on a specific set of signs and symptoms.

To improve diagnostic and treatment practices for management of DS associated with treatment with IDH-inhibitors (IDH DS), data for adverse events meeting diagnostic criteria for DS will be reviewed and assessed by a Differentiation Syndrome Review Committee.

Clinical Assessment of Subjects for signs and symptoms of IDH-inhibitors differentiation syndrome

Due to the heterogeneity of clinical symptoms and differences in adverse events reporting practices (e.g., symptoms of suspected IDH DS reported in place of DS diagnosis), exact incidence of Differentiation Syndrome in subjects treated with IDH-inhibitors has not been determined. In the clinical trial conducted for Idhifa's approval, at least 14 percent of patients experienced differentiation syndrome

As it has been reported by the Study Investigators, IDH DS is more likely to manifest within 10 days to 5 months after the start of treatment, or after re-initiation of the study drug following prolonged treatment interruption (e.g., >3 weeks) in subjects who are not in complete remission. In some cases, symptoms re-appeared after cessation of treatment for the initial manifestation of IDH DS.

Signs and Symptoms

In clinical trials with IDH inhibitors, DS has been described in two categories of severity:

MPN-RC A Phase II Open-label Study of Combined Ruxolitinib and Enasidenib Sinai in Patients with Accelerated/Blast-phase Myeloproliferative Neoplasm or Chronic-

phase Myelofibrosis with an IDH2 Mutation

(Myeloproliferative Neoplasms Research Consortium [MPN-RC] 119) Severe IDH-Differentiation Syndrome

Based on presence of any of the below listed factors, with, or without symptoms of moderate severity IDH DS

- New or worsened progressive dyspnea; hypoxia with increasing demands for supplemental oxygen; respiratory distress, without definitive etiology or refractory to treatment for the initially suspected cause
- Radiologic evidence of new or worsened bilateral pulmonary involvement (infiltrates or opacities) with or without presence of infection, refractory to treatment with anti-infectives (antibiotics, antivirals, antifungals) that was not attributed to another cause
- Radiologic evidence of new or worsened pleural or pericardial effusion that has no definitive etiology or is refractory to treatment for the initially suspected cause.

Moderate Severity IDH Differentiation Syndrome

Based on presence of at least 2 of the below listed factors, in absence of signs of severe IDH DS

- Unexplained fever $\geq 38^{\circ}C (100.4^{\circ}F)$
- New or worsened peripheral edema without definitive etiology, or rapid weight gain (e.g., > 5 kg/11 pounds)
- Rash of unknown origin
- New or worsened bone pain or arthralgia without other clear etiology
- Lymphadenopathy
- Increase in serum creatinine (e.g., >2-fold from baseline)

Conditions that may co-occur with differentiation syndrome

- Commonly co-occur: Leukocytosis in the absence of an infectious process
- Infrequently co-occur: Laboratory Tumor Lysis Syndrome (TLS), or TLS associated with increased serum creatinine level, in settings of rapidly increasing blood cell count (leukocytosis)
- Rarely co-occur: Coagulopathy in the setting of increased blood cell count

Management of subjects with suspected IDH inhibitors-differentiation syndrome

Conditions consistent with signs and symptoms of IDH DS but refractory to treatment for the initially suspected cause(s), or that worsen within the first 48 hours after treatment initiation, should be managed as potential IDH DS.

It is recommended that the measures indicated below are undertaken at the earliest manifestations of suspected IDH DS.

- Patients with severe or rapidly progressing IDH DS should be hospitalized for continued observation
- In case of uncertainty with the diagnosis, e.g. presence of less specific symptoms of moderate severity IDH DS, patients should be closely monitored, as condition may rapidly exacerbate
- Corticosteroids should be promptly initiated at a suggested dose 10 mg of dexamethasone IV every 12 hours until complete resolution of IDH DS, after which the dose can be progressively reduced in the next few days or weeks
- The study drug may be withheld at the investigator's discretion. Due to long half-life of the IDH-inhibitors, treatment interruption may not immediately reverse symptoms of IDH DS. Potential for drug-drug interaction between IDH inhibitor and treatments initiated for management of IDH DS should be considered, when making decisions about study drug treatment interruption. If interrupted, study drug treatment may be reinitiated at the original or reduced dose once the signs and symptoms resolve and the subject's clinical condition improves.

A Phase II Open-label Study of Combined Ruxolitinib and Enasidenib Sinai

in Patients with Accelerated/Blast-phase Myeloproliferative Neoplasm or Chronicphase Myelofibrosis with an IDH2 Mutation

(Myeloproliferative Neoplasms Research Consortium [MPN-RC] 119)

- If renal dysfunction or severe pulmonary symptoms requiring intubation or ventilator support persist for more than 48 hours after initiation of systemic corticosteroids, interrupt enasidenib treatment until signs and symptoms are no longer severe
- In subjects with elevated WBC, prompt initiation of hydroxyurea is suggested, as per standard local practices (e.g., dose of 2 to 3g PO twice or three times daily for WBC >30x10⁹/L)
- In cases of severe leukocytosis, use of leukapheresis may be appropriate
- For substantial fluid accumulation, initiation of furosemide may be appropriate, as per local standard practice
- Pericardial effusion a less common symptom of IDH DS can be life threatening condition requiring urgent intervention
- Subjects with increasing serum creatinine levels should be evaluated for TLS
- Subjects experiencing rapid increase in peripheral blood cells should be monitored for disseminated intravascular coagulopathy and hemorrhages
- Imaging techniques such as standard or high-resolution CT or chest X-ray are useful in establishing a diagnosis of IDH DS. However, chest X-ray is less sensitive in detecting early radiological signs of IDH DS associated changes.

Immediate communication with the Study Co-Chairs is encouraged for guidance regarding treatment.

MPN

Mount The Ti A Phase II Open-label Study of Combined Ruxolitinib and Enasidenib Sinai in Patients with Accelerated/Blast-phase Myeloproliferative Neoplasm or Chronicphase Myelofibrosis with an IDH2 Mutation

(Myeloproliferative Neoplasms Research Consortium [MPN-RC] 119)

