8.1 INCLUSION CRITERIA

- 1. Willing and able to adhere to the study visit schedule and all protocol requirements
- 2. Subjects must be \geq 18 years at the time of signing the Informed Consent Form (ICF).
- 3. Diagnosis of:
- a. Accelerated-phase (≥ 10% blasts in PB or BM) or blast-phase (≥ 20% blasts in PB or BM) myeloproliferative neoplasm (with history of prior myelofibrosis, polycythemia vera, or essential thrombocythemia)
 - b. Previously treated patients with myelofibrosis with persistent disease or progressive disease (persistent or progressive splenomegaly, leukocytosis, anemia, or thrombocytopenia) with intermediate-1 or greater risk disease according to 2013 International Working Group (IWG) criteria, and 4-9% circulating blasts.
- 4. Demonstration of an IDH2 mutation.
- 5. Platelet count \geq 75,000 X 10⁹/L for chronic phase myelofibrosis patients.
- 6. Prior therapy with either ruxolitinib or enasidenib is permitted, but not a combination of ruxolitinib and enasidenib.
- 7. Patients with chronic phase myelofibrosis on ruxolitinib must be on the drug for at least 3 months and on a stable dose for at least one month.

in Patients with Accelerated/Blast-phase Myeloproliferative Neoplasm or Chronicphase Myelofibrosis with an IDH2 Mutation

(Myeloproliferative Neoplasms Research Consortium [MPN-RC] 119)

- 8. Subjects must have an Eastern Cooperative Oncology Group (ECOG) performance status of 0 to 2. ECOG 3 status will be allowed if attributable to MPN.
- 9. Patients must have adequate organ function as demonstrated by the following:
 - a. Direct bilirubin ≤ 2.0 mg/dL, unless due to Gilbert's disease or current elevations in direct bilirubin associated with existing enasidenib use.
 - b. Serum creatinine< 2.0 mg/dL.

MPN-RC

- c. ALT and AST \leq 3x upper limit of normal (unless transaminitis is considered to be related to MF).

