20.1 ACCELERATED / BLAST-PHASE COHORT

Primary endpoint: The primary endpoint of this study is best overall response, defined as partial response or better (CR+PR+Cri), and will be defined as the best response within 6 cyclesof combination therapy. All patients meeting the eligibility criteria who have signed a consent form and have begun treatment will be evaluable for response. Any evaluable patient not meeting the definition for response will be deemed as having a non-response.

Design: The largest overall response rate where the proposed combination treatment regimen would be considered ineffective in this patient population is 5%, and the smallest response rate that would warrant subsequent studies with the proposed regimen is 25%. This is based on retrospective analysis applying the 2013 IWG Response Criteria to patients treated with ruxolitinib¹. A Simon's two-stage minimax design will be employed to test the null hypothesis that the true overall response rate in this patient population is at most 5%.

Decision Rule: Enter 13 patients into the study. If 0 responses are observed in the first 13 patients (Stage 1), we may consider this regimen ineffective in the patient population and the trial will close due to a lack of efficacy. If 1 or more responses are observed in the first 13 evaluable patients, we will proceed to Stage 2 and enroll an additional 7 patients onto the study for a total of 20 patients. After completion of both stages, if 3 or more responses out of the 20 patients are observed, the combination therapy will be considered promising for further investigation.

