22. DATA ANALYSIS PLANS

22.1 PRIMARY ENDPOINT

Overall response rate (ORR): The overall response rate will be estimated by the number of patients that attain a response (defined above per cohort) by 6 cycles of combination therapy divided by the total number of treated eligible patients. A two-sided 95% confidence interval for the true overall response rate will be calculated according the exact binomial method.

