22.2 SECONDARY ENDPOINTS

To additionally assess the efficacy of the combination of ruxolitinib with enasidenib in patients with accelerated or blast-phase disease after 6 cycles of combined therapy using complete (CBR) or partial blast response (PBR). CBR and PBR will be defined according to Appendix A. This will be calculated similarly to the primary endpoint for the MPN-AP/BP cohort.

To assess the efficacy of the combination of ruxolitinib with enasidenib in patients with PMF, post-PV MF, or post-ET MF in chronic phase and 4-9% blasts as assessed by the modified 2013 International Working Group (IWG) Response Criteria, after 6 months of combined therapy. This will be calculated similarly to the primary endpoint for the MPN-AP/BP cohort.

Adverse events: All eligible patients that have been initiated treatment will be included in the calculation of adverse event rate(s). The maximum grade for each type of adverse event will be tabulated for each patient, and frequency tables will be reviewed to determine patterns. Additionally, the relationship of the adverse event(s) to the study treatment will be taken into consideration. Adverse events will be summarized overall and by cohort.

Overall Survival (OS) will be defined as the time from first treatment with the ruxolitinib/enasidenib combination to death by any cause. Patients will be considered censored at the last known date alive, if death is not documented. OS will be estimated using the Kaplan-Meier method.

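### The complete blast response rate, as defined, may count accelerated/blast-phase patients who had no circulating blasts at baseline

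*Combined protocol and SAP*

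**What the plan says.** **Entry.** Section 8.1 (Inclusion Criteria, item 3a) admits "Accelerated-phase (≥ 10% blasts in PB or BM) or blast-phase (≥ 20% blasts in PB or BM) myeloproliferative neoplasm". Either site is enough, and no minimum blood blast count is set.

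**Definition.** Appendix A (34.1) defines complete blast response as "Absence of circulating peripheral blood blast count with residual features of chronic-phase MPN maintained for at least 28 consecutive days". The next row defines partial blast response (PBR) as "Reduction to <4% blast count in peripheral blood with residual features of chronic-phase MPN maintained for at least 28 consecutive days". Neither row states a marrow limit, and the residual-features phrase is not defined.

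**Analysis.** Section 22.2 states: "CBR and PBR will be defined according to Appendix A. This will be calculated similarly to the primary endpoint for the MPN-AP/BP cohort". For the primary endpoint, Section 22.1 takes the number of responders "divided by the total number of treated eligible patients" and an exact two-sided 95% interval.

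**Other use.** The Study Schema (Section 3) lists CBR among the responses on which AP/BP patients continue treatment after cycle 6.

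**The concern.** A response rate should count patients in whom something changed. The PBR row is worded as a reduction, so a patient already below 4% and unchanged does not meet it. The CBR row describes a state, not a change. A patient who entered with marrow blasts of 10% or more and none in blood satisfies its blast criterion on day 1.

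At stake is what the CBR rate means. If some AP/BP patients enter on marrow alone, the rate mixes clearance on treatment with the way patients qualified. A reader could not separate the two from the planned summary. The mix of entry routes will be known only after enrolment, so the rule should be fixed before the data are seen.

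**Working it through.** **1. The plan's own figures.** The documents give no rate, power or sample size for CBR. The only design calculation for this cohort is Table 6, for the primary endpoint: 13 patients, then 7 more; stop at 0 of 13; promising at 3 or more of 20. With true rate p:

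- P(early termination) = (1 − p)^13
- P(promising) = sum over x = 1 to 13 of P(X₁ = x) × P(X₂ ≥ 3 − x), with X₁ ~ Bin(13, p) and X₂ ~ Bin(7, p)

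| p | Early termination: computed (stated) | Promising: computed (stated) |
|---|---|---|
| 0.05 | 0.513 (0.51) | 0.074 (0.07) |
| 0.10 | 0.254 (0.25) | 0.317 (0.32) |
| 0.15 | 0.121 (0.12) | 0.586 (0.59) |
| 0.20 | 0.055 (0.05) | 0.786 (0.79) |
| 0.25 | 0.024 (0.02) | 0.903 (0.90) |

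Table 6 reproduces (0.05498 rounds to 0.05). CBR does not enter it.

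**2. Inputs for CBR.**

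- N = 20, the maximum evaluable AP/BP patients (Section 21).
- k = patients with no blood blasts at baseline who stay clear for 28 days and are judged to have residual chronic-phase features. Not in the documents; assumed 0 to 6.
- q = true clearance rate in the other 20 − k patients. Not in the documents; assumed 0 to 30%.

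**3. Rate as written.** Rate = [k + (20 − k)q] / 20. The excess over q is k(1 − q)/20, so each such patient adds (1 − q)/20, at most 1/20 = 5 percentage points.

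| k | q = 0 | q = 10% | q = 20% | q = 30% |
|---|---|---|---|---|
| 0 | 0% | 10% | 20% | 30% |
| 2 | 10% | 19% | 28% | 37% |
| 4 | 20% | 28% | 36% | 44% |
| 6 | 30% | 37% | 44% | 51% |

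For example, k = 4 and q = 20% gives (4 + 16 × 0.20)/20 = 7.2/20 = 36%.

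**4. In counts, with exact (Clopper-Pearson) 95% intervals, for k = 4.**

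- No true clearance: as written 4/20 = 20.0% (5.7–43.7%); among patients with baseline blood blasts 0/16 = 0% (upper limit 20.6%).
- Three true clearances: as written 7/20 = 35.0% (15.4–59.2%); among patients with baseline blood blasts 3/16 = 18.8% (4.0–45.6%); over all treated, with the four counted as not having CBR, 3/20 = 15.0% (3.2–37.9%).

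**5. Precision cost.** At an observed 25%, 5/20 has the interval 8.7–49.1% (width 40.4 points) and 4/16 has 7.3–52.4% (width 45.1 points), about 4.7 points wider.

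**The case against.** The strongest reply is that CBR needs more than a clear blood film: residual features of chronic-phase MPN must also be present for 28 days. Section 8.1 treats 10% or more blasts in blood or marrow as accelerated phase. Appendix A's progression row describes "Progression from chronic-phase disease (< 10% blasts) to blast-phase (≥ 20% blasts) disease on two separate CBCs within 28 days". On that reading a patient whose marrow stays at 10% or more is not back in chronic phase and is not a CBR. This is a fair reading, and it is why the point is that CBR may count such patients, not that it does. It does not close the gap. The phrase is undefined, the figure below 10% stands only in the progression row and is judged on blood counts, and no marrow test is attached to CBR.

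A second reply is that a change was plainly meant. Section 12.0 makes the clearing of blood blasts in AP/BP patients a milestone that prompts a marrow, and PBR is worded as a reduction. Both bear on intent, but neither amends the CBR definition, and Section 22.2 points to Appendix A alone.

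A third reply is that the size is assumed throughout. That stands: with k = 0 nothing changes, and counting every patient without baseline blood blasts is an upper bound.

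Three stronger readings are tempting and are not supported.

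- A reader might infer that PBR is wrongly diluted by patients already below 4%. Keeping them in as non-responders is the plan's stated and conservative convention.
- A reader might infer that the go/no-go decision is inflated. CBR has no threshold or alpha and is not part of the Simon rule.
- A reader might extend the worry to the primary endpoint, because one route to partial response in Appendix B has no marrow item. That route is otherwise strict, its frequency in AP/BP patients is unknown, and Section 20.1 ties the design rates to the same criteria: "This is based on retrospective analysis applying the 2013 IWG Response Criteria to patients treated with ruxolitinib". No type I error inflation is shown.

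**Conclusion.** The point holds in a limited form. Three parts of the plan combine: entry on blood or marrow blasts, a CBR definition with no baseline or change condition, and a denominator of all treated eligible patients. Together they let a patient who never had circulating blasts be scored as a complete blast response. The effect is at most 5 percentage points per such patient at N = 20, and nil if there are none. It rests on an unknown number of marrow-only entrants and on how the residual-features phrase is applied to them. It concerns the reading of a secondary endpoint; the primary endpoint, the Simon rule and Table 6 stand as written. The repair is cheap enough that it should be made before analysis.

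**What to change.** In Section 22.2 only:

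- Calculate the CBR rate among treated eligible AP/BP patients with baseline blood blasts above 0, taken from the screening blood count with differential (Section 14.1). Report how many are excluded, and label the result a peripheral-blood response.
- For the all-treated rate, and for any combined CBR-or-PBR rate, keep all treated eligible patients in the denominator and count those without baseline blood blasts as not having CBR.
- Leave the PBR denominator as planned. The rate among patients at 4% or more at baseline may be added.

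The change is an analysis rule and does not edit the Appendix A definition, because the Study Schema also uses CBR for continuing treatment. It needs no new data. The cost is a smaller denominator and a somewhat wider interval, as in step 5 of the working.

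Two reconciliations are separate from this rule:

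- The Study Schema and Appendix A should be reconciled on how CBR is used for continuation.
- Table 4 footnote 7 lets the treating physician omit marrows with no cohort limit. Section 15 schedules the cycle 4 marrow for all accelerated patients and the cycle 7 marrow for all patients, and Section 19.2 and Table 5 footnote 4 give discretion only for chronic phase. These should be reconciled on whether AP/BP marrows may be omitted.

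No treatment rule is proposed here.
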